# ATLASense RAPHAEL PolyMonitor – NIBP detection

The ATLASense RAPHAEL PolyMonitor detects NIBP at up to 1 minute intervals, and can derive the NIBP as an average over multiple measurements, or as a single NIBP measurement. The latency period between measuring these intervals and calculating an average for data recording and display is ~ 1 second when employing a local server.

# ATLASense RAPHAEL PolyMonitor – Temperature detection

The ATLASense RAPHAEL PolyMonitor detects skin temperature at up to 1 minute intervals, and derives measurements as an average based on multiple interval measurements. The latency period between measuring these intervals and calculating an average for data recording and display is ~ 1 second when employing a local server.

### CARESCAPE™ Monitor B850 - HR Detection

This multiparameter high acuity patient monitor is intended for use in multiple areas within a health care facility. Within the perioperative setting it is indicated for monitoring of multiple different hemodynamic parameters. However, for our study we will be acquiring data from its ECG monitoring function, and calculated HR. The heart rate will be measured at 1 minute intervals and then compared with time-matched HR acquired through the ATLASense PolyMonitor.

### GE Alsys CS2™ - RR Detection

The Aisys CS2 is functionally integrated ventilation, respiratory monitoring, and breathing system. Module bays allow for the physical integration of legacy Datex-Ohmeda patient monitors and supports mounting of other GE Healthcare monitors, including the CARESCAPE™ Monitor B850. The Aisys CS2 Anesthesia System is intended to provide general inhalation anesthesia and ventilatory support to a wide range of patients. Respiratory rate is calculated with this system from the frequency of peak (end tidal) CO2 measurements per minute. A breath is defined as a change in the CO2 signal that exceeds 1% (8 mmHg). All concentrations are measured and displayed breath by breath.

#### CARESCAPE™ Monitor B850 – Non-Invasive Blood Pressure Measurement

The CARESCAPE Monitor B850 employs the oscillometric technique for blood pressure measurement. In brief, this technique involves inflation of the cuff to a preset pressure. The pressure is then gradually reduced. With every arterial pulse wave there is a small rise and fall in volume within the vessel. This creates an increase and subsequent decrease in the pressure within the encircling blood pressure cuff, which can be detected using a solid-state transducer . Various proprietary algorithms then calculate the mean arterial pressure (MAP), diastolic, and systolic blood pressures. The CARESCAPE™ Monitor B85 employs the use of the DINAMAPTM SuperSTAT advanced NIBP algorithm from GE Healthcare.

#### CARESCAPE™ Monitor B850 – Arterial Line Blood Pressure Measurement

In patients with an arterial line placed during surgery, the CARESCAPE™ Monitor B850 will be used to monitor blood pressure. The CARESCAPE™ Monitor B850 employs an invasive blood pressure module which is able to transmit data obtained from the Arrow® arterial catheterization device. the Arrow® ASK-4500-HFH3 arterial catheterization device permits access to peripheral arterial circulation, and allows for

hydraulic coupling between the arterial circulation and a Wheatstone bridge piezoresistive transducer. This transducer converts the change of pressure transmitted within the arterial catheter with each heart contraction into a change of current which can then be displayed on the CARESCAPE™ monitor. The monitor filters the raw signal from the transducer and converts it into a visual waveform. Various proprietary algorithms then calculate the mean arterial pressure (MAP), diastolic, and systolic blood pressures.

### **CARESCAPE™ Monitor B850 – Temperature Measurement**

The Vyaire M1024215VY temperature sensor is a disposable device which can be inserted into a patient's esophagus and transmit core body temperature measurements at 1-minute intervals. The Vyaire M1024215VY has a direct input in order to display temperature information on the CARESCAPE™ Monitor B850.

#### Project Timeline

The primary end-point of the study is the collection of 14,303 time-matched HR and RR data pairs to power the study for 95% level of agreement (N = 14,303). This would require approximately 238 hours of intraoperative data collection if 1-minute intervals are used for time-matched data pairs. We estimate that 60-70 patients will need to be recruited based on surgical procedures with anticipated durations of 2-5 hours. Data collection is estimated to take approximately 3 months. Data analysis, and manuscript preparation is estimated to take an additional 6 months.

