monitors. Finally, this study will provide insight into the logistics of intraoperative use of the PolyMonitor.

The ATLASense Raphael PolyMonitor will be placed on the patient's left chest mid sternal line in the operating room. Traditional physiologic monitors described above will also be placed on the patient in the operating room. Data will be collected via the ATLASense system and through the traditional operating room monitors, and this data will be time matched through synchronization of the monitors post hoc. The time matched data pairs will undergo statistical analysis post hoc.

We anticipate that this study will validate the intraoperative HR and RR measured through the ATLASense Raphael PolyMonitor, providing adequate data points for statistical analysis with 95% limits of agreement, bias, and data loss/gaps. Success is also the logistical lessons learned for using this monitor in the intraoperative setting.

This study will provide a foundation for further investigation into the use of the ATLASense Raphael PolyMonitor as a tool for early detection and predictive modeling of patient physiological deterioration. With further study, this device has the potential to replace multiple traditional monitors, provide individualized data capture to build a predictive model for each patient and may extend perioperative physiologic monitoring beyond the operating room and recovery areas to a patient's home.

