# 3. STUDY PROCEDURES

#### Study Design and Outcomes

This will be a prospective observational study comparing HR and RR of intraoperative surgical patients simultaneously recorded by standard intraoperative monitors and the ATLASense RAPHAEL PolyMonitor. Funding for this study will be provided internally. This study will fall under regulatory oversight by the FDA.

This study will consist of an initial chart review of patients scheduled to undergo elective procedures at Henry Ford Hospital – Main Campus from October 2021, to December 2021. The study team will review their medical record in EPIC prior to their scheduled procedure and screen them to ensure that they meet all eligibility requirements. Patients will be contacted at least one week prior to their scheduled

procedure to provide them with a brief introduction to the study. If they are interested, they will be sent an Informed Consent Form via mail or email (whichever is their preference). This will ensure that the patients have adequate time to review the consent form and ask questions prior to their procedure. They will then be consented in person prior to their procedure and given a copy of the signed consent form.

Our **primary study aim** is to determine if the ATLASense RAPHAEL PolyMonitor can reliably measure intraoperative HR and RR as compared to traditional intraoperative monitors. In order to evaluate this aim, our primary outcome will be bias and precision (95% limits of agreement) of HR and RR of the PolyMonitor compared with the traditional monitors. It is hypothesized that the ATLASense RAPHAEL PolyMonitor will provide HR and RR measurements within ± 10% of the reference monitor or ± 3 breaths/min or ± 5 beats/min .

A secondary outcome that will examined include technical reliability in terms of data loss occurrences, and data gap duration. Additional secondary outcomes include reliability in detecting bradycardia and tachycardia, as well as bias and precision (95% limits of agreement) of skin temperature and NIBP of the PolyMonitor compared with traditional monitors.

Further lessons include the logistics of employing this PolyMonitor in intraoperative setting including device placement, surgical practices that may impede data collection (body placement, etc), device placement, patient feedback on wearable, and patient positioning considerations.

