#### **Statistical Analysis**

The data pairs of HR and RR measurements obtained in 1-minute intervals derived from the wireless sensors and the traditional physiologic monitors will be analyzed using the Bland and Altman method for repeated measurements . The Bland and Altman method will also be used to account for within-subject variation by correcting for the differences across patients and the variance of differences between the average differences. The bias (mean difference) between the ATLASense RAPHAEL PolyMonitor sensors and reference monitor and the 95% limits of agreement (± 1.96 SD) will be determined for both HR and RR data.

PolyMonitor bradycardia and tachycardia alert notifications will be time matched with the HR measurements from the traditional monitor. Reliability in determining tachycardic and bradycardic events will be assessed by calculating sensitivity, specificity, positive predictive value and negative predictive value from paired data. True positive tachycardia will be defined as HR > 100 BPM via the traditional monitor. True positive bradycardia will be defined as HR < 60 BPM via the traditional monitor. Based on the data points from our primary aim (N=14303), we have 99% power to detect a change in sensitivity from 0.5 to 0.8 using a two-sided binomial test and 99% power to detect a change in specificity from 0.5 to 0.8 using a two-sided binomial test. The target significance level is 0.05. The prevalence of tachycardia and bradycardia is assumed to be 0.01 to  $0.02^{2,7}$ .

Data pairs for skin temperature and NIBP obtained in 1 to 5 minute intervals derived from the wireless sensors and the traditional physiologic monitors will be analyzed using the Bland and Altman method for repeated measurements . The Bland and Altman method will also be used to account for within-subject variation by correcting for the differences across patients and the variance of differences between the average differences. The bias (mean difference) between the ATLASense RAPHAEL PolyMonitor sensors and reference monitor and the 95% limits of agreement (± 1.96 SD) will be determined for both HR and RR data. Sample size calculation was estimated based on the primary study aim.

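### No confidence interval is planned for the bias or the limits of agreement, and a target of 14,303 pairs is described as power although precision rests mainly on 60-70 patients

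*Combined protocol and SAP*

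**What the plan says.** The Project Timeline in section 3 makes the study's end-point the "collection of 14,303 time-matched HR and RR data pairs to power the study for 95% level of agreement". It converts this to recording time, "This would require approximately 238 hours of intraoperative data collection if 1-minute intervals are used for time-matched data pairs", and then to patients: "We estimate that 60-70 patients will need to be recruited based on surgical procedures with anticipated durations of 2-5 hours".

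The Statistical Analysis section says of the basis for this number only that "Sample size calculation was estimated based on the primary study aim". The available text gives no power, SD of the differences, expected bias, target interval width or within-patient correlation for the primary aim.

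For the analysis, the one-minute HR and RR pairs "will be analyzed using the Bland and Altman method for repeated measurements", with a stated correction for within-subject variation. The bias and "the 95% limits of agreement (± 1.96 SD) will be determined for both HR and RR data". No confidence interval is mentioned for either.

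Study Design and Outcomes gives the yardstick. The hypothesis is that the device will provide "HR and RR measurements within ± 10% of the reference monitor or ± 3 breaths/min or ± 5 beats/min". The section 1 abstract expects the study to succeed by "providing adequate data points for statistical analysis with 95% limits of agreement, bias, and data loss/gaps", which is an anticipated result rather than a sizing argument.

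**The concern.** Two things are run together in the sizing statement. The 95% in limits of agreement is the share of differences that the limits are meant to contain. It says nothing about how precisely the study will estimate those limits, and it is not a power. The count is also of pairs, while the independent units are patients. Minute-by-minute differences from one patient share that patient's electrode contact, body habitus, position and rhythm, so 200 or so of them carry less information than the same number from different people.

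This would matter little if the results showed their own precision, but the plan stops at point estimates. The primary aim is to say whether HR and RR agree closely enough with the reference, and a numerical criterion is given. If an estimated limit falls close to it, a reader has no means of telling whether the true limit is inside or outside. A headline of 14,303 pairs may then suggest more certainty than 60-70 patients can give.

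**Working it through.** **The plan's own figures.** 14,303 / 60 = 238.4 hours, which matches the stated 238. Pairs per patient are 14,303 / 70 = 204.3 to 14,303 / 60 = 238.4. That is 3.4 to 4.0 hours per patient, inside the stated 2-5 hours. These figures are consistent with one another.

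**Can 14,303 be rebuilt?** No, because its inputs are not given. The sensitivity and specificity power statement does not generate it: that statement takes N = 14,303 as given. At a prevalence of 0.01-0.02 there would be 143-286 events, whereas 99% power for 0.5 against 0.8 needs only about 44 events, or 2,200-4,400 pairs.

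**Precision if pairs were independent** (in SDs of the differences, N = 14,303):

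- Bias: 1.96 / sqrt(N) = 0.016 SD.
- Each limit: 1.96 × sqrt(1/N + 1.96² / (2(N − 1))) = 0.028 SD.

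**Precision with repeated pairs.** Take n = 65 patients and m = 220 pairs each (14,300 in all), total variance 1, and pairs exchangeable within a patient. The ICC is an assumption, shown as a range.

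- E(MSB) = (1 − ICC) + m × ICC and E(MSW) = 1 − ICC
- Var(bias) = E(MSB) / (nm)
- Var(S²) = 2E(MSB)² / ((n − 1)m²) + (1 − 1/m)² × 2E(MSW)² / (n(m − 1)), and Var(S) = Var(S²) / 4
- Half-width of a limit = 1.96 × sqrt(Var(bias) + 1.96² × Var(S))

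Worked at ICC 0.1: E(MSB) = 0.9 + 22 = 22.9. Var(bias) = 22.9 / 14,300 = 0.001601. Var(S²) = 0.000339 + 0.000113 = 0.000451 (from unrounded terms), so Var(S) = 0.000113. The limit half-width is 1.96 × sqrt(0.001601 + 3.8416 × 0.000113) = 0.088 SD.

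| Assumed ICC | Bias, half-width (SD) | Limit, half-width (SD) | Limit with 60 / 70 patients (SD) |
|---|---|---|---|
| Independent pairs | 0.016 | 0.028 | – |
| 0.01 | 0.029 | 0.037 | 0.038 / 0.037 |
| 0.1 | 0.078 | 0.088 | 0.092 / 0.086 |
| 0.5 | 0.172 | 0.243 | 0.253 / 0.234 |

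**Serial correlation.** Consecutive minutes are unlikely to be exchangeable. Simulating 65 × 220 with AR(1) error within patients, at an assumed correlation of 0.8 to 0.9, gives a limit half-width of about 0.07 to 0.10-0.11 SD at ICC 0.01, 0.11 to 0.13 SD at ICC 0.1, and 0.25 to 0.26 SD at ICC 0.5. The exchangeable figures are therefore too favourable where the ICC is low, and nearly unchanged where it is high.

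**The case against.** The strongest reply is that the plan already handles repeated measurements where it counts. The named method separates between- and within-patient variation, so the limits themselves are appropriate. That stands. A reader might infer that the analysis ignores clustering, or that intervals would be computed as if pairs were independent. The documents support neither: they name a repeated-measures method and plan no interval at all.

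A second reply is that the effect may be small. If a limit were 5 beats/min, the SD would be 5 / 1.96 = 2.55 beats/min and the half-widths about 0.09, 0.23 and 0.62 beats/min at the three exchangeable ICCs. Nothing in the documents says a limit is expected near the criterion. This also stands, and it is why the point is minor. Nor should ±5 beats/min be read as the whole HR criterion: the criterion also has a ±10% part, which is wider than 5 above 50 beats/min (8 at 80 beats/min). The wording concerns measurements within a range and states no rule that the limits must lie inside it.

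A third reply is that the number of patients is given. It is: 60-70, with case lengths that fit. The same pair count would need about 48 or 119 patients only if every operation lasted exactly 5 hours or 2 hours (14,303 / 300 = 47.7; 14,303 / 120 = 119.2), so the plan does not leave the number wide open.

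None of these replies supplies an interval for the primary result, and citing a repeated-measures method does not commit the sponsor to reporting one.

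**Conclusion.** The concern holds in a limited form, as a minor point. The sizing statement treats the coverage of the limits as if it were power and counts pairs rather than patients. The planned primary results carry no measure of precision.

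A reader might go further and infer that 14,303 is wrong, or that the study is too small. The documents do not support that. The inputs are absent, so the figure can be neither confirmed nor refuted, and there is no target width against which 60-70 patients could be called too few.

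The size depends on an ICC and a serial correlation that the documents do not give. Over the assumed range, the half-width of a limit runs from about 1.3 times the independent-pairs value (0.037 / 0.028) to about 9 times (0.243 / 0.028). It changes what can be concluded only if a limit falls near the criterion.

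**What to change.** 1. In Statistical Analysis, add 95% confidence intervals for the bias and for both limits, for HR and for RR, from a bootstrap that resamples whole patients. This allows for unequal case lengths and for serial correlation without having to model either. Show the intervals alongside the criterion in Study Design and Outcomes, including its ±10% part.

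2. In Project Timeline, replace the phrase about powering the study with a statement that precision is set mainly by the planned 60-70 patients, with 14,303 pairs (about 238 hours) as the expected yield. Any precision figure given there should state the assumed ICC and the within-patient correlation structure, because the exchangeable figures alone can be too favourable. If a derivation of 14,303 exists, this is the place for it.

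The cost is wording in two sections, a little more analysis, and a stated precision that looks less favourable. No extra patients or data are needed.

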# Protection of Privacy

Subject name and MRN will be recorded out of necessity during subject screening, recruitment and data acquisition so that data can be appropriately tracked. However, the PI and Co-investigators will take appropriate steps to minimize risk to the subject and ensure protected health information is secured. The information will be de-identified by a broker from HFHS Data Analytics prior to being given to the study team for analysis. The identifiable information will be stored in a secure REDCap database and will be destroyed as soon as possible after the record maintenance period. All study data will remain on secure HFHS password-protected computers and stored on secure HFHS servers.

#### **Statistical Analysis**

The data pairs of HR and RR measurements obtained in 1-minute intervals derived from the wireless sensors and the traditional physiologic monitors will be analyzed using the Bland and Altman method for repeated measurements . The Bland and Altman method will also be used to account for within-subject variation by correcting for the differences across patients and the variance of differences between the average differences. The bias (mean difference) between the ATLASense RAPHAEL PolyMonitor sensors and reference monitor and the 95% limits of agreement (± 1.96 SD) will be determined for both HR and RR data.

PolyMonitor bradycardia and tachycardia alert notifications will be time matched with the HR measurements from the traditional monitor. Reliability in determining tachycardic and bradycardic events will be assessed by calculating sensitivity, specificity, positive predictive value and negative predictive value from paired data. True positive tachycardia will be defined as HR > 100 BPM via the traditional monitor. True positive bradycardia will be defined as HR < 60 BPM via the traditional monitor. Based on the data points from our primary aim (N=14303), we have 99% power to detect a change in sensitivity from 0.5 to 0.8 using a two-sided binomial test and 99% power to detect a change in specificity from 0.5 to 0.8 using a two-sided binomial test. The target significance level is 0.05. The prevalence of tachycardia and bradycardia is assumed to be 0.01 to  $0.02^{2,7}$ .

Data pairs for skin temperature and NIBP obtained in 1 to 5 minute intervals derived from the wireless sensors and the traditional physiologic monitors will be analyzed using the Bland and Altman method for repeated measurements . The Bland and Altman method will also be used to account for within-subject variation by correcting for the differences across patients and the variance of differences between the average differences. The bias (mean difference) between the ATLASense RAPHAEL PolyMonitor sensors and reference monitor and the 95% limits of agreement (± 1.96 SD) will be determined for both HR and RR data. Sample size calculation was estimated based on the primary study aim.

Technical performance will be analyzed by the duration of data loss and the total amount of data loss. Reliability will be defined as the time until the first occurrence of data loss (defined as duration of a gap within the data of 2 min, 15 min, 1 hour or 4 hours) and the overall amount of data loss. The time to first occurrence of data loss will be analyzed with Kaplan-Meier survival plots. Data analysis will be performed by a statistician from the

HFHS Public Health Sciences.

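### The planned HR result is one pooled bias and one constant pair of limits, so it mainly describes 60–100 BPM and cannot show at which heart rates the error lies

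*Combined protocol and SAP*

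**What the plan says.** Section 3, Study Design and Outcomes, defines the primary endpoint without reference to HR level: "our primary outcome will be bias and precision (95% limits of agreement) of HR and RR of the PolyMonitor compared with the traditional monitors". The hypothesis there is that readings fall "within ± 10% of the reference monitor or ± 3 breaths/min or ± 5 beats/min".

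Section 3, Statistical Analysis, states that the 1-minute pairs "will be analyzed using the Bland and Altman method for repeated measurements". The planned summary is: "The bias (mean difference) between the ATLASense RAPHAEL PolyMonitor sensors and reference monitor and the 95% limits of agreement", the latter taken as ±1.96 SD, for HR and RR alike. The repeated-measures step is there to "account for within-subject variation by correcting for the differences across patients". It deals with variation between and within patients, not with heart rate. Neither section mentions regression on the mean, a ratio or log scale, or limits by HR range.

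The same section takes reference HR above 100 BPM as tachycardia and below 60 BPM as bradycardia, and plans sensitivity, specificity and predictive values of the device alerts. "The prevalence of tachycardia and bradycardia is assumed to be 0.01 to" 0.02. The text does not say whether that figure is per condition or for both together.

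The HR Detection section for the device reports accuracy of ±1% or ±2 BPM, whichever is greater, for resting HR only, with a detection range of 30–240 BPM.

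**The concern.** One constant pair of limits describes agreement well only if bias and spread are similar at all heart rates. The plan does not establish this. Its agreement margin is partly proportional to rate, the device accuracy figure is partly proportional in form, and no accuracy is stated away from rest.

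If nearly all pairs come from normal rates, the pooled figures mainly describe normal rates. A device that drifts at high or low rates could then be reported with acceptable pooled limits. Conversely, an error confined to a few abnormal minutes could widen the limits and make the device look worse than it is at normal rates. Either way the primary aim, whether HR is measured reliably during surgery, would have no answer by rate. Section 1 presents the device as a foundation for early detection of deterioration, where abnormal rates matter most.

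**Working it through.** **1. The plan's own figures.** 14,303 / 60 = 238.4 hours, matching the stated 238. Abnormal pairs per condition: 14,303 × 0.01 = 143 and 14,303 × 0.02 = 286. Exact two-sided binomial power for sensitivity 0.5 versus 0.8 at alpha 0.05 exceeds 0.9999 with 143 positives, consistent with the stated 99% (44 positives would be enough). The total of 14,303 cannot be reproduced, because no SD or target precision is given.

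**2. Share of pairs in 60–100 BPM.**
- Prevalence per condition: 1 − 2 × 0.01 = 98% (14,017 pairs), down to 1 − 2 × 0.02 = 96% (13,731).
- Prevalence combined: 99% (14,160) down to 98% (14,017).

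**3. Effect on the pooled result.** Let a fraction f of minutes carry a constant error e, and let the random difference have mean 0 and SD s throughout. Then

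- pooled bias = f·e
- pooled SD = √(s² + f(1−f)e²)
- limits = f·e ± 1.96 × pooled SD

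The documents give no s, so 1 to 2.5 BPM is an assumption. If the stated ±2 BPM is a 95% bound, s is about 1; if it is an SD, s is 2. Setting the upper limit to 5 BPM gives the largest same-direction error e (BPM) that leaves both limits within ±5:

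| s (BPM) | f = 1% | f = 2% | f = 4% |
|---|---|---|---|
| 1.0 | 22.3 | 15.5 | 10.7 |
| 1.5 | 19.5 | 13.5 | 9.3 |
| 2.0 | 14.7 | 10.1 | 6.9 |
| 2.5 | 4.0 | 2.5 | 1.6 |

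On the per-condition reading, 1–2% means one tail is wrong and 2–4% means both are. If the errors have opposite signs and equal shares in the two tails, the pooled bias is 0 and slightly larger errors pass: 16.6 to 11.7 BPM at s = 1, and 11.2 to 7.9 at s = 2, for f from 2% to 4%.

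**4. Worked example.** s = 1.5, f = 2%, e = 12. Bias = 0.24. SD = √(2.25 + 0.0196 × 144) = 2.25, half-width 4.41, limits −4.17 to +4.65. At a true rate of 110 BPM, an error of 12 exceeds both 5 BPM and 10% (11 BPM).

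**5. The limits do react.** With s = 1.5 the clean limits are ±2.94. An 18 BPM error in 1% of minutes moves them to −4.40 and +4.76. A repeated-measures simulation with 65 patients gave nearly the same: −4.38 to 4.74 with the affected minutes in 5 patients, and −4.30 to 4.63 with them in 20. With s = 2 (clean ±3.92), a 20 BPM error in 2–4% of minutes gives bias 0.4–0.8 and half-width 6.7–8.6. The limits then fail ±5 although 96–98% of minutes are unaffected.

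**6. Which remedy locates the error.** I simulated an 18 BPM step above 100 BPM only (s = 1.5, 1–2% of pairs per tail, normal-range mean 77 and SD 7–9; all assumed). A straight-line regression of difference on mean reported a bias of about +4 to +8 at 120 BPM, and a false −2.5 to −4.4 at 50 BPM. Summaries by reference HR range returned about 18 above 100 BPM and about 0 below 60.

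**The case against.** A reader might infer that large errors at abnormal rates are invisible in the planned analyses, or barely show. The documents and the arithmetic do not support that. It fits the bias, but the limits respond to the squared error: in step 5 they widen by more than half. Of the six combinations of s = 1, 1.5 or 2 with f = 1% or 2%, an 18 BPM error stays inside ±5 in only two (s = 1 and s = 1.5, both at 1%). At s = 2.5 almost nothing is hidden.

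Four further points stand in part:

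- **The scenario is severe.** It assumes that every affected minute is wrong by the same amount in the same direction, and nothing in the device description predicts this.
- **The margin is a tolerance.** It is not a statement that error grows with rate. If either criterion suffices, above 100 BPM more than 10 BPM is tolerated, so some hidden errors (10.1 BPM at s = 2, f = 2%) are essentially acceptable there. Below 60 BPM, 10% is under 6 BPM, so an error of 7 BPM fails both criteria. The device's ±1% exceeds ±2 BPM only above 200 BPM; the resting-only restriction matters more. Nor do the documents say that success means pooled limits inside ±5.
- **The alert analysis covers part of the gap.** Errors that carry a reading back across the threshold lower sensitivity. A true 110 shown as 128 remains a correct alert, and its size is not measured.
- **The prevalence wording is ambiguous.** Applying it per condition and per minute is an inference. The combined reading puts a still larger share of pairs at normal rates.

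**Conclusion.** The point holds in a limited form. The plan provides one HR bias and one constant-width pair of limits, weighted 96–99% to 60–100 BPM on its own prevalence, and nothing that shows how agreement varies with rate. Abnormal-range errors are diluted in the bias and unlocated in the limits.

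How much can be concealed depends on an SD that the documents do not give: roughly 7–22 BPM at an SD of 1–2 BPM, over 1–4% abnormal minutes, but only about 2–4 BPM at 2.5 BPM. These figures assume a constant error in every affected minute and take ±5 BPM as the yardstick for the limits. The structural point, that pooled limits cannot locate error, needs neither assumption. The change should be made before analysis; it does not invalidate the pooled result as a summary of the minutes actually observed.

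**What to change.** Keep the pooled limits and add the following to Statistical Analysis:

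- Repeated-measures bias and 95% limits for HR by reference range: <60, 60–100 and >100 BPM, the plan's own thresholds.
- For each range, the percentage of pairs within the stated margin, the number of pairs and patients, and confidence intervals that allow for clustering within patients. Say how the ±10% and ±5 BPM criteria combine.
- A plot of difference against the mean of the two methods. Any regression on the mean should be flexible, not a single straight line (step 6).
- A statement that the HR agreement conclusion applies only to ranges whose limits meet the margin.
- Whether the 0.01–0.02 prevalence is per condition or combined, and whether it is per minute.

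The cost is SAP wording and extra output from data already being collected. The downside is imprecision in the tails. With 143–286 pairs per tail, the 95% half-width around each limit would be 1.96 × 1.71/√n, or 0.28 to 0.20 of that range's SD, if minutes were independent. It will be wider because minutes cluster within 60–70 patients, and wider again if the prevalence is combined. A range may have too few patients to support a conclusion, and the report should then say so.
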